4.1 BENEFIT AND RISK ASSESSMENT

The available aggregate nonclinical and clinical data from the sarilumab development program in RA have demonstrated a potent anti-inflammatory effect and significant clinical benefit for patients with active RA via blockade of the IL-6 signaling pathway, which is also thought to play a key role in the pathogenesis of GCA. Therefore, treatment of GCA patients with sarilumab may lead to clinical benefits as observed in patients with active RA. This likely benefit with sarilumab is further supported by the pivotal GiACTA trial (a phase 3 study which evaluated efficacy and safety of tocilizumab in GCA patients [9]) that resulted in the approval of a similar IL-6 inhibitor, tocilizumab, for the treatment of GCA. Because of the similarity of sarilumab to tocilizumab and a study design that mirrors the successful GiACTA trial, it is expected that the current study will demonstrate a similar efficacy for sarilumab in GCA. Sarilumab is already approved for the treatment of rheumatoid arthritis in multiple countries.

Based on the safety profile of sarilumab available to date and other biological DMARDs, important identified risks include serious infections, neutropenia and hypersensitivity reactions; important potential risks to be considered with sarilumab administration, consistent with this class of therapy, include laboratory abnormalities and the potential clinical consequences, such as thrombocytopenia and the potential risk of bleeding, clinically evident hepatic injury with elevated hepatic transaminases, and lipid abnormalities and potential increased risk of major adverse cardiovascular event (MACE). Other potential important risks include increased risk of malignancy and gastrointestinal perforation. Various risk mitigation strategies are either built into the eligibility criteria (Section 7.1 and Section 7.2) to exclude those with conditions that may jeopardize their safety or into other sections of the protocol (Section 10.4 and Section 10.7) for monitoring and management of certain risks/adverse events (eg, neutropenia, thrombocytopenia, liver transaminase elevation, etc).

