11.4.3.1 Analysis of adverse event data

Treatment-emergent AEs, treatment-emergent SAEs, TEAEs leading to treatment discontinuation and treatment-emergent AESIs will be summarized for each treatment group based on MedDRA coding of verbatim terms reported by Investigators.

Adverse event incidence tables will present by system organ class (SOC) (sorted by internationally agreed order), high-level group term (HLGT), high level term (HLT) and preferred term (PT) sorted in alphabetical order for each treatment group, the number (n) and percentage (%) of patients experiencing an AE. Multiple occurrences of the same event in the same patient will be counted only once in the tables within a treatment period. The denominator for computation of percentages is the safety population within each treatment group.

Treatment-emergent AESI, by AESI category and PT, will show number (%) of patients overall, sorted by decreasing incidence of PT within each AESI category. The AESIs include, but are not limited to, the following categories and details of the MedDRA coding will be provided in the statistical analysis plan: Neutropenia, thrombocytopenia, infections, hepatic disorders, diverticulitis/GI ulcerations/GI perforations, elevation in lipids, systemic allergic reactions, malignancy, autoimmune or drug-induced lupus like syndrome and demyelinating disorders.

Death: The following deaths summaries will be generated:

- Number (%) of patients who died by study period (TEAE, on-study) summarized on the safety population by treatment received
- Death in nonrandomized patients or randomized and not treated patients
- TEAE leading to death (death as an outcome on the AE CRF page as reported by the Investigator) by primary SOC, HLGT, HLT and PT showing number (%) of patients sorted by internationally agreed order of SOC and alphabetic order of HLGT, HLT, and PT.

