11.4.3.2.2 Assessment of potential drug-induced liver injury

The LFT, namely ALT, AST, alkaline phosphatase and total bilirubin, are used to assess possible drug induced liver toxicity. The proportion of patients with PCSA values at any post-baseline visit by baseline status will be displayed by treatment group for each parameter. The proportion of patients with PCSA values at any post-baseline visit will also be displayed by duration of exposure for each treatment group.

Time to onset of the initial ALT elevation ($> 3x$ ULN), time to onset of the initial AST elevation ($> 3x$ ULN), time to onset of the initial total bilirubin elevation ($> 2x$ ULN), and time to first observation of ALT $> 3x$ ULN or Total Bilirubin > 2 ULN (whichever comes first) will be analyzed using Kaplan-Meier estimates, using the midpoint of the time interval between the first assessment showing the elevation and the previous assessment, presented by treatment group. A graph of distribution of peak values of ALT versus peak values of total bilirubin will also be presented. Note that the ALT and Total bilirubin values are presented on a logarithmic scale. The graph will be divided into 4 quadrants with a vertical line corresponding to $3x$ ULN for ALT and a horizontal line corresponding to $2x$ ULN for total bilirubin.

Summarize the normalization by parameter (to ≤ 1 ULN or return to baseline) of elevated LFT by categories of elevation (1- $< 3x$, 3x, 5x, 10x, 20x ULN for ALT and AST, 1.5 x ULN for Alkaline phosphatase, and 1.5x and 2x ULN for total bilirubin), with following categories of normalization: never normalized, normalized after IMP discontinuation. Note that a patient will be counted only under the maximum elevation category. 1 - 3, 3 - 5, 5 - 10, 10 - 20, > 20 .

The incidence of liver-related AEs will be summarized by treatment group. The selection of preferred terms will be based on standardized MedDRA query (SMQ) Hepatic disorder. Time to liver-related treatment discontinuation and time to liver death may also be provided based on hepatic disorder SMQ.

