Appendix L General guidance for the follow up of laboratory abnormalities by Sanofi

[figure not shown]
Note:

•The procedures described in the above flowchart are to be discussed with the patient only in case the event occurs. If applicable (according to local regulations), an additional consent (e.g., for HIV testing) will only be obtained in the case the event actually occurs.

•For individuals of African descent, the relevant value of concern is $<1000/\text{mm}^3$

Neutropenia is to be recorded as an AE only if at least 1 of the criteria listed in the general guidelines for reporting AEs in [Section 10.5.3](#) is met.

[figure not shown]
THROMBOCYTOPENIA

Note:

The procedures above flowchart are to be discussed with the patient only in case described in the the event occurs. If applicable (according to local regulations), an additional consent (e.g., for HIV testing) will only be obtained in the case the event actually occurs.

[figure not shown]
Thrombocytopenia is to be recorded as an AE only if at least 1 of the criteria listed in the general guidelines for reporting AEs in [Section 10.5.3](#) is met.

- In **ANY CASE**, **FOLLOW** the instructions #1 to #8 listed in the box below.
1. **INFORM** the medical monitor/CRA
 2. **COMPLETE** the specific form for “Liver Injury”
 3. **INVESTIGATE** specifically for malaise with or without loss of consciousness, dizziness, and/or hypotension and/or episode of arrhythmia in the previous 72 hours; rule out muscular injury
 4. **PERFORM** the following tests:
 - LFTs: AST, ALT, alkaline phosphatase, total and conjugated bilirubin, and prothrombin time /INR
 - CPK, serum creatinine, complete blood count
 - Anti-HAV IgM, anti-HBc IgM, anti-HCV and HCV RNA, anti-CMV IgM and anti-HEV IgM antibodies
 - Auto-antibodies: antinuclear, anti-DNA, anti-smooth muscle, anti-LKM
 - Depending on the clinical context, check for recent infection with EBV, herpes viruses, and toxoplasma
 - Hepatobiliary ultrasonography (can be completed by other imaging investigations if needed)
 5. **CONSIDER** consulting with hepatologist
 6. **CONSIDER** patient hospitalization if INR >2 (or PT <50%) and/or central nervous system disturbances suggesting hepatic encephalopathy
 7. **MONITOR** LFTs
-If investigational medicinal product is discontinued due to ALT increases as closely as possible to every 48 hours until stabilization, then every 2 weeks until return to normal (<2 x ULN) or baseline for at least 3 months, whichever comes last

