- Grade 2: ≥ 1.0 Giga/L- < 1.5 Giga/L.
- Grade 3: ≥ 0.5 Giga/L- < 1.0 Giga/L.
- Grade 4: < 0.5 Giga/L.

Thrombocytopenia

The incidence of thrombocytopenia by maximal grade (lowest platelet count reported during the TEAE period) as defined below will be summarized.

- ≥ 75 Giga/L-100 Giga/L.
- ≥ 50 Giga/L- < 75 Giga/L.
- ≥ 25 Giga/L- < 50 Giga/L.
- < 25 Giga/L.

Hepatic disorders

The liver function tests, namely AST, ALT, ALP, and total bilirubin are used to assess possible drug-induced liver toxicity. The proportion of patients with PCSA values at any post-baseline visit by baseline status will be displayed by treatment group for each parameter. The proportion of patients with PCSA values at any post baseline visit may be displayed by duration of exposure for each treatment group.

A graph of distribution of peak values of ALT versus peak values of total bilirubin will also be presented. Note that the ALT and total bilirubin values are presented on a logarithmic scale. The

graph will be divided into 4 quadrants with a vertical line corresponding to 3x ULN for ALT and a horizontal line corresponding to 2x ULN for total bilirubin.

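### The SAP omits, without declaring it, the protocol's summary of whether raised liver tests normalised and its pooled count of liver-related adverse events

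*SAP*

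**What the plan says.** Protocol 11.4.3.2.2 plans to summarise normalisation (to 1 x ULN or below, or back to baseline) "of elevated LFT by categories of elevation", "with following categories of normalization: never normalized, normalized after IMP discontinuation". Each patient counts once, under the highest category reached. The section also states: "The incidence of liver-related AEs will be summarized by treatment group". The terms are fixed: "The selection of preferred terms will be based on standardized MedDRA query (SMQ) Hepatic disorder". Only time to liver-related discontinuation and time to liver death are worded as optional. Protocol 11.4.3.1 names hepatic disorders among the AESI categories and says that "details of the MedDRA coding will be provided in the statistical analysis plan". Protocol 4.1 counts "clinically evident hepatic injury with elevated hepatic transaminases" among the important potential risks.

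The hepatic paragraph of SAP 2.4.5.3 begins: "The liver function tests, namely AST, ALT, ALP, and total bilirubin are used to assess possible drug-induced liver toxicity". It plans PCSA proportions by baseline status, an optional display by duration of exposure, and the ALT-bilirubin plot. Time-to-onset curves come earlier in the same section. Elsewhere the SAP uses normalisation only for CRP, and it mentions no SMQ. SAP 1.6 is introduced as the summary of changes from the protocol and names no liver or other safety analysis.

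**The concern.** Incidence tables say how many patients had a raised liver test, not what happened next. For a drug whose protocol names hepatic injury as a risk, the clinical reading depends on whether an elevation came back down, and whether it did so on drug or only after stopping. The protocol planned to report this and the SAP does not.

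The SMQ summary answered a second question: how many patients per group had any liver-related event. Individual term rows cannot be added up to give that, because a patient with two terms is counted in both rows.

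The omission is also undeclared. Someone who reads SAP 1.6 to learn what changed would conclude that the liver analyses stand as the protocol wrote them.

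**Working it through.** No formula is at issue. The check sets Protocol 11.4.3.2.2 against the SAP item by item.

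| Protocol 11.4.3.2.2 | SAP |
|---|---|
| (a) PCSA proportions by baseline status and by duration of exposure | Kept in 2.4.5.3; the by-exposure display becomes optional |
| (b) Kaplan-Meier time to ALT, AST and bilirubin elevation, and to the first of ALT >3 x ULN or bilirubin >2 x ULN | Kept in 2.4.5.3 without the ALT-or-bilirubin composite; >5 x ULN curves added |
| (c) Plot of peak ALT against peak bilirubin | Kept in 2.4.5.3 |
| (d) Normalisation by maximum elevation category | Absent |
| (e) Liver-related AEs by group, Hepatic disorder SMQ | Absent |

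Of five blocks, three are kept (two of them reduced) and two are gone.

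**Is the change declared?** SAP 1.6 covers the Week 52 cohort, the Week 24 endpoint, GTI, missing data, significance level, multiplicity and subgroups. The incomplete assessments it cites concern efficacy, ADA and biomarkers, not laboratory safety. SAP 2.4.5.3 also adds safety outputs that the protocol section lacks, such as platelet grades and lymphocyte curves, so a general trimming of laboratory analyses does not explain the loss.

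**Do the retained outputs classify recovery?**
- PCSA and shift tables count abnormality at any time in the TEAE period. They show occurrence, not outcome.
- By-visit summaries are group statistics. Under SAP 2.5.4 an unscheduled retest enters only when the window holds no scheduled value.
- Flagged listings show the values but assign no outcome.

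**Do they give one liver-event count?** SAP 2.4.5.1 tabulates TEAEs by SOC, HLGT, HLT and PT. For the liver, SAP Table 5 has two investigator-ticked AESIs: ALT at or above 3 x ULN, and ALT increase leading to permanent discontinuation. No table pools the SMQ terms, and Table 5 does not supply the hepatic coding that Protocol 11.4.3.1 deferred to the SAP. SAP Appendix C refers to safety guidelines that are not in the documents, so it cannot be taken to restore either item.

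**Size.** The documents give no ALT rate. SAP Table 1 estimates 28 + 14 = 42 sarilumab patients. With an assumed 5% to 10% above 3 x ULN: 0.05 x 42 = 2.1 and 0.10 x 42 = 4.2, or about 2 to 4 patients.

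**The case against.** The strongest reply is that little is lost, and much of it stands.

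- **Liver safety is reported.** A reader might infer that liver events survive only as scattered SOC and PT rows, or that repeat tests feed no summary. Neither is so. SAP 2.4.5 takes all TEAE-period evaluations into the PCSA counts, including unscheduled and repeat tests, and SAP 2.5.5 takes unscheduled values into the shift tables. SAP Appendix B has a combined criterion of ALT >3 x ULN with bilirubin >2 x ULN. Each AESI category gets patient incidence, seriousness, discontinuation, death and relatedness.
- **Recovery data will be incomplete.** A reader might infer that every outcome has already been collected. Appendix L asks for tests "as closely as possible to every 48 hours until stabilization, then every 2 weeks until return to normal", but only after discontinuation for ALT increases, and it defines normal there as <2 x ULN, whereas the protocol's summary uses 1 x ULN or below. Protocol 10.7.2 adds repeats at least weekly for a confirmed ALT of 3 to 5 x ULN. The readable text has no such rule for lesser elevations. SAP 1.1 cuts follow-up to 6 weeks, and the flow chart schedules no chemistry after EOT.
- **The protocol table is not ready to use.** Its two outcomes leave no row for normalisation on treatment or after a temporary interruption, and the same paragraph gives two differing sets of elevation bands.
- **With 2 to 4 cases, most cells of a table would be empty.** A listing may serve better.

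These points limit the consequence and shape the remedy. They do not supply the two missing outputs or the missing declaration. The SAP does not give sparse liver data as a reason for leaving them out.

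**Conclusion.** The point holds as an undeclared omission of two committed liver outputs, with limited consequences. What the trial cannot report as planned is a classification of whether elevations resolved, and one count per group of patients with any liver-related TEAE.

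The stronger inference, that liver injury would go unreported or that a complete set of recovery data lies unused, is not supported, given the retained tables and the shortened follow-up. No efficacy estimate, test or analysis population changes, and safety reporting was descriptive throughout. The figure of 2 to 4 patients rests on an assumed 5% to 10% rate and on an estimated group size. This is a worthwhile low-cost improvement to a terminated trial of 83 patients, not a flaw in its main analysis.

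**What to change.** In SAP 2.4.5.3 add:

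1. A per-patient listing, or a short table by treatment group, of patients with raised ALT, AST, ALP or bilirubin. Show the maximum elevation on one consistent set of bands, and classify the outcome as normalised on treatment or after temporary interruption, normalised after permanent discontinuation, not normalised, or unknown at last follow-up. State the criterion (the protocol's is 1 x ULN or below, or return to baseline). Use all available values, including unscheduled and post-treatment ones.
2. One row per treatment group for patients with any TEAE in the Hepatic disorder SMQ.

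If either is left out, declare and justify it in SAP 1.6. Both items concern reporting only and touch no rule for testing, interrupting or resuming treatment.

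The cost is a small amount of programming on data in hand, with no new collection. The yield is modest: few patients, some of them with unknown outcome.

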2.4.5.4 Analyses of vital sign variables

The summary statistics (including number, mean, median, SD, minimum, and maximum) of all vital signs variables (vital signs values and changes from baseline) will be calculated for each visit or study assessment (baseline, each post baseline time point, endpoint) by treatment group.

The incidence of PCSAs at any time during the TEAE period will be summarized by treatment group whatever the baseline level and/or according to the following baseline status categories:

- Normal/Missing
- Abnormal according to PCSA criterion or criteria

Listings will be provided with flags indicating the PCSA values.

2.4.6 Analyses of pharmacokinetic variables

All the PK analyses will be performed using the PK populations including only the sarilumab treated patients.

Serum concentrations of functional sarilumab will be summarized using descriptive statistics (including number, arithmetic and geometric means, SD, standard error of the mean, coefficient of variation, minimum, median, and maximum) for each visit. The samples will be considered non-eligible for these analyses if the previous dosing time is <11 days or >17 days before the sampling time for every other week regimens. Concentrations below the lower limit of quantification (LLOQ) will be set to zero for samples at baseline (i.e., predose at Week 0). Other post-treatment concentrations below LLOQ will be replaced by LLOQ/2. In addition, serum concentrations of functional sarilumab will be summarized using descriptive statistics mentioned above by immunogenicity status for each visit.

Listings of serum concentration will be provided for each individual patient. The listings include subject identification (ID), gender, age, first dose date, visit number, categorized time point (0 for trough level and 1 for pre-dose), date/time of previous dose, PK sampling date/time, duration since first dose (days), duration since previous dose (dd:hh), serum concentration (ng/mL).

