- l CRP and ESR results will be blinded to Investigator (except screening and baseline). ESR kits will be provided by the central laboratory while the test will be performed locally at the site, results will be blinded to Investigator and staff directly involved in management of study patient, except safety assessor.
- m Urinalysis dipstick: specific gravity, pH, glucose, ketones, blood, protein, nitrite, leukocytes, urobilinogen and bilirubin. If any parameter on the dipstick is abnormal, a urine sample should be sent to the central laboratory for testing. If positive for proteins, microscopic analysis is performed by central laboratory.

- n* Human immunodeficiency virus antibodies (a separate local Informed Consent may need to be obtained if applicable); Hepatitis B: HBsAg, total HB core Ab, Hep B Surface Antibody, and Hep B viral DNA (if necessary); Hepatitis C: HCV-antibodies.
- o* In women of child-bearing potential.
- p* Additional sample is to be drawn 4-7 days after Wk 24 dosing.
- q* Immune cell phenotyping may be performed in only a subset of patients as determined by IRT system.
- r* Future use Samples (for consented patients only).
- s* Pharmacogenetic Research Informed Consent for collecting and sequencing DNA and RNA samples has to be obtained before any sampling. One DNA (at baseline) and RNA sample (predose) for sequencing sampling time point at baseline and V3 are needed.

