Sarilumab will be administered in non-affected skin subcutaneously in the abdomen or thigh when self-injected or in upper arm (lateral side) when injected by a professional or a non-professional caregiver. It is preferred that SC injection sites be alternated between the 4 quadrants of the abdomen (except the navel or waist area) or the thigh (front and side). Each drug administration requires a single injection.

Patients and/or their non-professional caregivers will be trained to prepare and administer study drug at the baseline visit. This training must be documented in the subject's study file. The study staff should review the patient's self-administration technique at Visit 2 (Week 0). For doses not given at the study site, diaries will be provided to record information pertaining to those injections. If the patient is unable or unwilling to administer study drug, arrangements must be made for a qualified site personnel or a caregiver to administer study drug doses that are not scheduled to be given at the study site.

Dose regimen:

The IMP (sarilumab or matching placebo) should be administered every 14 days as per protocol IMP administration schedule, however an IMP administration time window of ± 3 days is permitted in exceptional circumstances (eg. Laboratory test result pending, or an ongoing adverse event (AE) or patient schedule difficulty). For subsequent IMP administrations the initial IMP administration schedule should be followed again (see [Table 1](#)).

Note: An interval of ≥ 11 days between 2 IMP doses must be maintained.

If the study visit is not performed at the site as scheduled, the dose will be administered as described above, either by the patient, qualified site personnel, and/or their caregiver(s).

On days when the patient has a study visit, the IMP will be administered after clinic procedures and blood collection.

Patients will be monitored for at least 30 minutes after each dose of sarilumab, or as per country specific requirements (eg, up to 2 hours) for any signs or symptoms of any medical events. In the case that the injection is administered by caregiver or self injection, patients should be instructed to monitor themselves for any signs or symptoms of any medical events.

The total duration of treatment is 52 weeks.

Dose modification/reduction:

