9.4.2.4 Pharmacokinetics parameters

Predose serum sarilumab concentrations at Week 0, sarilumab trough levels at Weeks 2, 4, 12, 16, 24, 52 and Week 58.

In addition, postdose sample will be taken 4 to 7 days after the Week 24/V9.

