For PK and ADA, the follow-up (i.e., 6-week post-treatment) measurement will be defined based on the sample collected at the follow-up visit (ie, Visit 13). The rests of PK and ADA measurements will be mapped to each visit using the visit window defined in [Table 9](#).

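### SAP 2.4.6 applies a trough-only 11–17 day rule to every by-visit PK summary, so the planned post-Week 24 and follow-up samples cannot qualify

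*SAP*

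**What the plan says.** SAP 2.4.6 plans descriptive statistics of functional sarilumab concentration for each visit in sarilumab-treated patients, and repeats them by immunogenicity status. It then sets the eligibility rule: "The samples will be considered non-eligible for these analyses if the previous dosing time is <11 days or >17 days before the sampling time". The sentence closes by referring to every-other-week regimens. No visit is exempted. The individual listings in the same section carry no stated filter, and their time-point code has two values only, trough and pre-dose.

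Protocol 9.4.2.4 names the planned times: a Week 0 pre-dose sample, "sarilumab trough levels at Weeks 2, 4, 12, 16, 24, 52 and Week 58", and a further one: "postdose sample will be taken 4 to 7 days after the Week 24/V9". The flow charts in both documents repeat the latter: "Additional sample is to be drawn 4-7 days after Wk 24 dosing".

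SAP Appendix H, Schedule H maps serum sarilumab taken on Days 141–266 to Week 24 and has no row for the post-dose sample. Below its table, Appendix H adds that for PK and ADA "the follow-up (i.e., 6-week post-treatment) measurement will be defined based on the sample collected at the follow-up visit" (Visit 13).

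SAP 2.5.4 resolves several values in one window by taking the scheduled measurement closest to the target day and, on a tie, the latest.

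**The concern.** The window fits a sample drawn just before the next fortnightly dose. Applied to all visits, it also judges samples that were never meant to be end-of-interval troughs. Protocol 9.4.2.4 may have encouraged this by listing Week 58 among the trough levels, although no dose is due near that visit.

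Nothing suggests that the samples were dropped on purpose. Protocol 11.4.4 plans by-visit summaries without such a filter. SAP 1.6, which lists departures from the protocol's analysis, names no omitted PK time point. Appendix H takes care to define the follow-up measurement that 2.4.6 then rules out.

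Measuring serum sarilumab is a stated secondary objective. The main PK tables would omit a planned mid-interval concentration and a planned off-treatment concentration. The loose window mapping could also cost some patients their Week 24 trough.

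**Working it through.** **1. Where the window comes from.** Protocol 8.1.1: the SC product "should be administered every 14 days as per protocol IMP administration schedule", and "an IMP administration time window of ± 3 days is permitted in exceptional circumstances". So 14 − 3 = 11 and 14 + 3 = 17, which reproduces the SAP's limits.

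**2. Gap from previous dose at each planned time.** Dose days are 1 + 14k for k = 0 to 25. The last is 1 + 14 × 25 = Day 351, which is Week 50, as the flow-chart footnote says.

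| Sample | Day | Previous dose | Gap (days) | Within 11–17? |
|---|---|---|---|---|
| Week 0 | 1 | none | – | rule does not reach it |
| Week 2 | 15 | 1 | 14 | yes |
| Week 4 | 29 | 15 | 14 | yes |
| Week 12 | 85 | 71 | 14 | yes |
| Week 16 | 113 | 99 | 14 | yes |
| Week 24 | 169 | 155 | 14 | yes |
| Post-Week 24 | 173–176 | 169 | 4–7 | no |
| Week 52 | 365 | 351 | 14 | yes |
| Week 58 | 407 | 351 | 56 | no |

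Two of the nine planned times fail.

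**3. Whether permitted variation rescues them.**
- Post-Week 24 sample, Week 24 dose withheld and sample still taken: the gap from Week 22 is 14 + 4 to 14 + 7 = 18–21 days. Not eligible.
- Week 58, with ±3 days on both visit and dose: 404 − 354 = 50 to 410 − 348 = 62 days. Not eligible.
- Week 58, had a dose been given at Week 52: 407 − 365 = 42 days, at least 404 − 368 = 36. Not eligible.
- Discontinuation plan (SAP 1.1), follow-up 6 weeks after stopping: about 42 days, or 39 if 3 days early. Not eligible.

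**4. Mapping of the post-dose sample.** Days 173–176 lie inside Schedule H's Week 24 window (141–266), as does the trough. Let the visit and dose fall on Day v, within 169 ± 3, and the extra sample on Day v + g with g = 4 to 7. For v below 169 the trough is 169 − v days from target and the extra sample is v + g − 169 days from it. With ties going to the later value, the extra sample is selected when v + g − 169 ≤ 169 − v, that is, when g ≤ 2 × (169 − v).
- v = 166: g ≤ 6. Samples on Days 170 and 171 are closer (1 and 2 days against 3). Day 172 ties at 3 and wins as the later.
- v = 167: g ≤ 4. Day 171 ties at 2 and wins.
- v = 168: g ≤ 2, so never. For v = 169 or later the trough is always the closer value.

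If mapping comes before the eligibility check, a displaced trough is replaced by a value that is then excluded, and the patient has no Week 24 value. If eligibility comes first, the trough survives. The SAP gives no order.

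**The case against.** The best defence concerns the follow-up sample. The rule is tied to every-other-week regimens, and a patient at Visit 13 is no longer being dosed. Appendix H could then be read as the specific provision that keeps the sample in. This is not convincing: both sarilumab arms are dosed every 2 weeks, so the qualifier excludes no one, and the rule counts days from the previous dose without requiring that dosing continues. Appendix H only assigns a sample to a visit. It does not say that the sample is exempt from 2.4.6, and it still serves ADA and the listings if the rule stands. The defence does not reach the 4–7 day sample at all.

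A second objection is that the closest-to-target bullet in SAP 2.5.4 mentions only efficacy, laboratory and vital-sign measurements in its parenthesis, so its use for PK is uncertain. That is fair. The sentence introducing the bullets does include PK, however, and no other selection rule is given.

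A third is that little depends on this. The trial stopped at 83 of 360 patients, and PK is descriptive with no test attached. That stands and limits the importance of the point.

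**Conclusion.** The rule is wrong as written. Taken as scheduled, the post-Week 24 and follow-up samples are non-eligible for the 2.4.6 summaries in every sarilumab-treated patient who gives them (SAP Table 1 estimates 28 + 14 = 42 such patients of 83). The displacement of the Week 24 trough is a narrower problem. It needs a visit on Day 166 or 167, the 2.5.4 selection rule applied to PK, and the extra sample counted as scheduled. The loss of a Week 24 value further requires mapping to precede the eligibility check. No efficacy or safety conclusion is affected.

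A reader might infer more than the documents support:
- *That the values are lost, or never summarised by ADA status.* The listings have no stated filter. SAP 2.4.8 plans its own by-visit concentration summary by ADA classification and also states none.
- *That these are the trial's only near-peak and only washout concentrations.* Neither document describes 4–7 days as near peak. Samples are also drawn around serious adverse events (protocol 9.4.2.1, SAP 2.1.6), and patients who stop treatment early are asked to keep their scheduled visits (protocol 10.4.4).
- *That the post-dose sample always loses to the trough in the Week 24 window.* It does at a Day 169 visit, but not in the early-visit cases worked out above.

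**What to change.** In SAP 2.4.6, limit the <11/>17 day rule to the on-treatment troughs at Weeks 2, 4, 12, 16, 24 and 52. Give the post-Week 24 sample and the follow-up sample their own summary rows, eligibility windows and listing codes. Since follow-up gaps will be about 42 days in some patients and 56 in others, show time since last dose beside that row.

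In Appendix H, keep the post-dose sample out of the Week 24 trough mapping. State in 2.5.4 that the selection rule covers PK, and whether eligibility is applied before or after mapping. Say in 2.4.8 whether the ADA-by-PK summary uses the same eligibility.

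The cost is a few sentences, two table rows and two codes. No new data are needed and the efficacy analyses are untouched.
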